Study Rationale	
Heart failure (HF) is prevalent in more than 6 million Americans and is a leading cause of hospitalizations. Active HF self-management reduces hospitalizations but patient adherence to HF self-care behaviors is poor. Data suggests that family involvement in the patient's care enhances patients' self-management.
 
Patient and family engagement is critical to obtaining the knowledge, skills, and confidence for effective self-management. Engagement is often manifested through asking questions, expressing concerns, and clarifying information from health care providers (HCPs). Engagement is generally low among individuals with HF.
 
Strategies such as pre-visit prompt lists can enhance patient and family engagement by encouraging patients and family members to ask relevant questions and discuss sensitive topics with HCPs. However, several important gaps in the literature exist. First, the effect of prompt lists on self-management has not been tested. Second, few studies have used them with family members. Lastly, prompt lists have not been tested in HF patients.

Study Objective(s)	The specific aims of this pilot study are to: 1) Develop a pre-visit question prompt list for use with HF patients and family members; and 2) Conduct a pre-post pilot study in up to 30 HF patients and family members to evaluate feasibility, acceptability, and effects of the prompt list on HF self-care behaviors (of patients and family members/caregivers), communication behaviors, and self-efficacy with communication.
Test Article(s) (If Applicable)	The question/topic prompt list is the main intervention in this study. A prompt list is a written document containing suggested questions that the family member and/or patient may want to ask the health care provider during the visit. A section is included for the patient to check which behaviors they would like for their family member to engage in during the visit and space is provided for the family member to check which behaviors they are willing to perform during the visit.
Study Design	Single group pre-post design
Subject Population	We will enroll adult patients with HF, family members, and HCPs. Patient Eligibility Ambulatory adult patients ≥ 30 years old

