3.4 Study Population. We will enroll HF patients, family members, and HCPs

Patient Eligibility

Ambulatory adult patients \geq 30 years old
Receive care in the UNC Cardiology or General Internal Medicine practice
Have a clinical diagnosis of HF
Currently prescribe a loop diuretic
Have a New York Heart Association class II-IV
Must speak English
Must have a working telephone or live with the patient

Family Member/Companion Eligibility

Must be at least 18 years old and able to give informed consent
Must be willing to participate in the intervention activities and provide informed consent
Must speak English
Must have a working telephone or live with the patient

Health Care Provider Eligibility

Must be an MD or advance practice provider (NP or PA) in the UNC cardiology or General Internal Medicine practice
Must be willing to have an enrolled patient visit audio-taped

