
Partners in Health Eligibility SCREENING FORM

The following form will be used to determine eligibility for Patients:

Partners in Health: Pilot test of a Pre-Visit Question Prompt List to Enhance Engagement of heart failure (HF) patients and Family Members During Medical Visits

Patient Eligibility Form

Research Assistant: _____

Study ID#: _____

QUESTIONS TO ASK PATIENT TO VERIFY ELIGIBILITY

DATE: _____

1. Is English your preferred language?"
YES NO
2. "Do you see a health care provider at the UNC Cardiology Clinic?"
YES NO
3. "Do you have a diagnosis of Heart Failure (or Diastolic Dysfunction)?"
YES NO
4. "Do you take a loop diuretic medication?" (e.g. Furosemide, Lasix, Bumetanide, Bumex, Demadex, Torsemide)
YES NO
5. "Do you take a thiazide diuretic medication?" (e.g. Hydrochlorothiazide, HydroDIURIL, Chlorothiazide, Diuril, Chlorthalidone, Metolazone, Zaroxolyn, Indapamide, Lozol)
YES NO
6. "What is your current age?"
7. "Do you require assistance with basic activities of daily living?"
YES NO
8. "Do you live in a nursing home or care facility?"
YES NO

(Patients who receive nursing home services (including help with basic activities of daily living are NOT eligible to participate; patients living independently in senior centers or independent living facilities ARE eligible)

9. Do you have a working telephone?
YES NO
10. Do you agree to have one of your visits with your provider audiotaped
YES NO
11. Symptom Assessment (Patient must answer "YES" to at least one question)

"Think about the last six months and the days you felt the worst.

So, on your worst days..."

1) "How many city blocks could you walk before getting short of breath?"

If states a specific number, has symptoms (Number _____ = symptoms)

YES

If says can walk as far as s/he wants—go to #2

NO

If unable to walk enough to answer question, go to 1a below

Unable to answer

2) "Did you have to walk at a slower pace than normal to keep from getting short of breath?"

If says Yes, has symptoms

YES

If says No—go to #3

NO

3) "If you had to rush or hurry, did you get short of breath?"		
If says Yes, has symptoms		YES
If says No—go to #4		NO
4) "How many flights of stairs could you climb without getting short of breath or needing to stop to catch your breath?"		
If less than 2 flights or needs to stop at 2 flights catch breath, has symptoms		YES
If can walk up 2 or more flights then is truly class I and does not have symptoms		NO

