(If unable to answer question 1 above, ask the following questions)		
1a) "Have you experienced swelling of the legs or ankles due to excess fluid?"	YES	NO
1b) "Do you sleep on more than one pillow at night to help you breathe easier?"	YES	NO

TO BE COMPLETED BY RESEARCH ASSISTANT ELIGIBILITY CRITERIA—for Heart Failure Patients

Patients must have ALL of the following eligibility criteria.

1. Relationship – Patient must be seen by a health care provider at the UNC Cardiology clinic at least one time before? YES
2. Diagnosis – Carry a clinical diagnosis of Heart Failure or Diastolic Dysfunction YES
3. Medications– Currently prescribed a loop or Thiazide diuretic. YES

Loop Diuretics: Bumetanide (Bumex®), Torsemide (Demadex®), Furosemide (Lasix®)

Thiazide Diuretics: Hydrochlorothiazide (HydroDIURIL®), Chlorothiazide (Diuril®), Chlorthalidone, Metolazone (Zaroxolyn®), Indapamide (Lozol®)

4. Symptoms – Have New Class II, III or IV symptoms now or in the past 6 months YES
5. Age – Over the age of 21 YES
6. Communication – Speak English and have adequate hearing to communicate and talk in person or on the phone. YES
7. Audiotaping – Must agree to have a visit audiotaped YES

INELIGIBILITY CRITERIA

Patients will be ineligible if they meet ONE of the following criteria:

1. Do not speak English
2. Have significant cognitive impairment (e.g. a diagnosis of dementia/severe cognitive impairment)
3. Have significant psychiatric impairment (e.g. schizophrenia)

4. Require assistance with Activities of Daily Living (ADL)
5. Live in a nursing home

IS THE PATIENT ELIGIBLE? (Circle one) ELIGIBLE INELIGIBLE

Partners In Health Eligibility SCREENING FORM

The following form will be used to determine eligibility for Family Members:

Research Assistant: _____

Study ID#: _____

QUESTIONS TO ASK INDIVIDUAL TO VERIFY ELIGIBILITY

1. "What is your current age?" _____
Family member must be at least 18 years old.

2. "What is the highest grade you completed?" _____
(If 6th grade or below, or if have knowledge that family member is illiterate, have witness present when signing consent)

3. Do you have a working telephone or live with the patient?
YES NO

4. "Is English your preferred language?"
YES NO

If family member does not speak English, then they are ineligible to participate.

The family member and the patient MUST answer YES to the following question for the visit companion to be eligible to participate.

Read the following definition to the participant:

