11 RECRUITMENT STRATEGY

11.1 CONSENT PROCESS

Recruitment will be completed by the Study Coordinator or other approved study personnel. Screening to determine eligibility to participate will take place via telephone or in a private location within the clinic. An IRB-approved eligibility form will be used by the RA. The informed consent process will occur in a private location within the clinic.

Potential participants will be given a description of the study in a clear, concise manner and given time to ask questions and have their questions answered by study personnel. Consent will be obtained immediately after the initial consent discussion; and will be obtained directly from the participant. An unsigned hard copy of consent documents (Consent, HIPAA) will be given to each participant for their records. This document will contain contact information for the study coordinator and the PI.

Potential participants (both patient and visit companion) will be given the choice of either reading the consent on their own, or having the consent read to them. If the consent form is read to the participant, the signature page will indicate that the consent was read to the participant. The consent form will describe the study including the potential risks and benefits and will explicitly state that if participants choose not to participate; their medical care at UNC will not be impacted in any way. In addition to the consent form, the HF patient will read a HIPAA authorization form. The patient will be informed that if they choose not to sign the HIPAA authorization form then they may not participate in the study. This information will also be on the written consent form.

The HF patient and the family member will have similar, but separate consent forms. Both the HF patient and the family member will be asked to consent to be audio-taped. The consent form for the family member will state that if s/he is a patient of the health care provider at UNC Hospitals, we will not access their protected health information (PHI) and thus, will not require patient authorization. Potential participants will be allowed to ask questions and have the answers, and the consent forms will then be signed. During this entire process, the PI will be available by pager or cell phone for questions. Copies of all consent documents will be given to participants.

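### The synopsis and Section 3.4 conflict with the Section 4 screening form on patient age, diuretic class and clinic, and Section 6.1 does not say which list defines eligible in the primary endpoint

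*Combined protocol and SAP*

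**What the plan says.** The synopsis, under Subject Population, sets the age criterion as "Ambulatory adult patients ≥ 30 years old", and Section 3.4 repeats it. On medication, Section 3.4 has "Currently prescribe a loop diuretic". On clinic, it has "Receive care in the UNC Cardiology or General Internal Medicine practice". The synopsis matches on both.

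The patient eligibility form in Section 4 has a checklist for the research assistant, and every item on it must be met. Its age item is "Age – Over the age of 21". Its medication item is "Currently prescribed a loop or Thiazide diuretic", followed by named drugs of both classes; a separate question to the patient asks about thiazides. Its clinic item is "Patient must be seen by a health care provider at the UNC Cardiology clinic at least one time before", and the matching patient question names only UNC Cardiology.

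The form is the working tool. Section 4 introduces it with "The following form will be used to determine eligibility for Patients", and Section 11.1 adds "An IRB-approved eligibility form will be used by the RA". It ends with an eligible/ineligible verdict to be circled.

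Section 6.1 defines the primary outcome as the proportion of eligible patients who enrol. It refers to neither list. Section 4.7 has the forms of people who refuse or are ineligible destroyed within a week, and promises only a list of names so that they are not approached again.

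**The concern.** These are different values for the same criterion in current text. The synopsis describes its list as the key criteria, which could explain items that appear only on the form, such as cognitive impairment, nursing-home residence or agreement to taping. It cannot explain two age limits, two diuretic rules or two clinic rules.

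Two things are at stake. The first is who enters: staff who follow the form could depart from Section 3.4 in both directions. The second is the primary endpoint: eligibility is its denominator, so two lists can give two rates from the same recruitment effort. Since the forms of non-enrolled people are destroyed, the rate could not be fully rebuilt later under the other list.

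**Working it through.** **Side by side**

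| Criterion | Synopsis and Section 3.4 | Screening form, Section 4 | Effect of following the form |
|---|---|---|---|
| Age | 30 or over | over 21 | admits patients over 21 and under 30, whom 3.4 excludes |
| Diuretic | loop | loop or thiazide | admits thiazide-only patients, whom 3.4 excludes |
| Clinic | Cardiology or General Internal Medicine | at least one earlier UNC Cardiology visit | rejects General Internal Medicine patients with no such visit, whom 3.4 admits |

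The form is wider on two criteria and narrower on one, so neither list is a subset of the other.

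**Site text.** Section 1 names the Cardiology and General Internal Medicine clinics as the setting. The script read after the baseline questionnaire and the provider-consent text in Section 11.1 name only the heart or Cardiology clinic at Meadowmont. The clinic conflict is therefore not confined to the form.

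**Does an earlier step remove the conflict?** Section 4.1 asks providers to confirm heart failure, to judge whether the patient may be approached, and to rate how often a companion attends. It mentions neither age, diuretic class nor clinic. It does not say which list drives the initial identification from the data warehouse, registry, chart audit or provider suggestions.

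**Effect on the primary rate (illustration only).** The document has no figure to reproduce and gives no counts. Assume 60 form-eligible patients, of whom 30 enrol: 30/60 = 50.0%. Let u be the form-eligible patients who fail Section 3.4, e those among them who enrolled, and v the patients who meet Section 3.4 but fail the form and so cannot enrol. Then

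rate under Section 3.4 = (30 − e) / (60 − u + v).

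- u = 0, v = 6: 30/66 = 45.5%.
- u = 3, e = 3, v = 0: 27/57 = 47.4%.
- u = 3, e = 0, v = 0: 30/57 = 52.6%.

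The rate can move either way. For scale, the Wald 95% half-width at 30/60 is 1.96 × √(0.5 × 0.5 / 60) = 12.7 points. The values of u, e and v are assumptions, and these results are examples, not bounds.

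**Can it be repaired afterwards from the surviving forms?** Surviving forms come mainly from enrolled patients. Take u = 6, of whom 3 enrolled and 3 refused, with v = 0. Full re-classification gives (30 − 3)/(60 − 6) = 27/54 = 50.0%. Re-classifying only the enrolled gives 27/(60 − 3) = 27/57 = 47.4%. The 3 refusers stay in the denominator, so the rate is too low by 2.6 points. Whenever some refusers fail Section 3.4, this error is downward. Patients rejected by the form (v) cannot be recovered from forms at all.

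**The case against.** The strongest reply is that the endpoint is less open than it looks. The form is stated to determine eligibility, it closes with a circled verdict, and the consent section says the assistant uses it. A sensible analyst would take the circled verdict as the meaning of eligible, and the missing cross-reference in Section 6.1 is then a drafting gap. This stands as the likely default. It remains an inference, and it would leave the primary endpoint resting on a population that Section 3.4 does not describe.

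A second reply is that the practical effect may be small. No counts are given, and nothing shows that patients under 30, thiazide-only patients or patients seen only in General Internal Medicine would reach screening. With providers consented at the Meadowmont Cardiology clinic, few of the last group might. Section 3.4 might also be applied at identification, before the form is used. This stands too: the correct word is that staff could, not would, enrol or reject against Section 3.4.

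A reader might infer that the conflict threatens the study's 50% aim. The document does not support that. Section 6.1 states that aim for screened patients, so a rate among eligible patients cannot be set against it directly.

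Section 4.1 does ask providers for reasons when they rule a patient out. That covers provider exclusions only, not failures on the form or refusals.

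**Conclusion.** The three conflicts hold as a matter of text, and no part of the document resolves them. Following the form can admit patients whom Section 3.4 excludes and reject patients whom it admits, and the denominator of the primary outcome depends on which list is used. The size and direction of any effect on the rate are unknown; the percentages above rest wholly on assumed counts.

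This should be fixed, but it is not critical. The study is a single-group pilot, and Section 6.3 disclaims hypothesis testing. A reader might infer that the primary endpoint cannot be computed, or that its result is already known to be biased. Neither follows: the form offers a workable default, and no counts show a bias. Three other questions would remain even if the lists matched and are separate points: eligible versus screened as the denominator, patients versus patients and companions as the unit, and how the rule that both dyad members must qualify enters the rate.

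**What to change.** 1. Reconcile Section 3.4, the synopsis and the screening form into one list. The sponsor decides which wording stands on age, diuretic and clinic.
2. Align the site text in Section 1, the post-baseline script and the provider-consent part of Section 11.1 with that list.
3. State in Section 6.1 that this list defines eligible for the primary endpoint.
4. Before any form is destroyed under Section 4.7, record a de-identified tally, by criterion, of the reason for each non-enrolment.
5. If screening has already begun, do not re-classify from surviving forms alone. Report the rate under the list actually applied, and describe enrolled patients who fall outside the reconciled list.

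The cost is one amendment with its IRB submission and one tally line per screened patient who does not enrol. No extra patients or study procedures are needed.

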During our conversation, I'll ask you questions about yourself, your visit companion, and your interactions with your doctor. Your "visit companion" is the family member or friend who comes with you to your health appointments. Your "doctor" is the doctor, nurse practitioner, or other health care provider who you usually see during your visit.

After completing the prompt and if the participant is able to conduct their data collection at that time, the RA/SC will collect their data either by using one of the following: 1) paper data collection materials; 2) the iPad REDCap application; or 3) by computer using the REDCap online data capture system. Regardless of the way in which the data is collected, each data collection will be administered uniformly to all participants.

Below are the **BASELINE QUESTIONNAIRES** with their respective variables for analysis for patients

List of measures included in this questionnaire:

1. Relationship with companion
2. Companion involvement
3. Closeness with companion
4. Health literacy
5. Knowledge of heart failure+
6. Self-care behaviors
7. Self-efficacy related to self-care
8. Perceived health status
9. Heart failure symptom severity
10. Communication with provider
11. Perceived efficacy in interactions with doctor
12. Perceived social support
13. Demographic/background questions

*Note that the Baseline Questionnaires **for companions** includes the following measures, which parallel the patient questionnaires:

List of measures included in this questionnaire:

1. Relationship with patient
2. Companion involvement
3. Closeness with patient
4. Knowledge of heart failure
5. Caregiver care behaviors
6. Self-efficacy related to patient care
7. Perceived efficacy in interactions with doctor
8. Demographics
9. Health literacy

Companion for visit with doctor

1. **Will you have a companion, such as a family member or friend, come with you to visit your doctor during this study? Variable name: accompanied**

- a. Yes
- b. No

IF NO:

- 2. Does someone usually go with you to your medical appointments? **Variable name: usual_accomp**
 - a. Yes
 - b. No

Relationship with Companion

[IF PARTICIPANT WILL NOT HAVE A COMPANION COME WITH THEM TO THEIR APPT, ASK ABOUT THE PERSON WHO USUALLY GOES WITH THEM. IF PARTICIPANT DOES NOT USUALLY HAVE A COMPANION COME WITH THEM TO THEIR APPT, SKIP AHEAD TO HEALTH LITERACY.]

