For these first few questions, please think about the person who will come with you to your medical appointment during this study [or who usually comes with you to your medical appointments]. This might be your spouse, your brother/sister, one of your children, or someone else.

- 1. **What is your relationship to this person? You are that person's ____.** **Variable name: relationship**
 - a. Spouse
 - b. Partner
 - c. Mother
 - d. Father
 - e. Brother
 - f. Sister
 - g. Daughter
 - h. Son
 - i. Friend
 - j. Other relationship. Please specify _____

Closeness with Companion

For the next two questions, please continue to think about the person who will come with you to your medical appointment during this study [or who usually comes with you to your medical appointments].

- 1. **Relative to all your other relationships (both same and opposite sex) how would you characterize your relationship with this person?** **Variable name: closeness_1**

Not close at all						Very close
0	1	2	3	4	5	6

2. Relative to what you know about other people's close relationships, how would you characterize your relationship with this person? **Variable name: closeness_2**

Not close at all 0	1	2	3	4	5	Very close 6
-----------------------	---	---	---	---	---	-----------------

Health Literacy

Now I have a couple of questions about how you handle hospital materials and forms.

1. How often do you have someone (like a family member, friend, hospital/clinic worker or caregiver) help you read hospital materials? **Variable name: reading_lit**

None of the time 0	A little of the time 1	Some of the time 2	Most of the time 3	All of the time 4
-----------------------	---------------------------	-----------------------	-----------------------	----------------------

2. How confident are you filling out forms by yourself? **Variable name: fill_forms**

Not at all confident 0	1	2	3	Extremely confident 4
---------------------------	---	---	---	--------------------------

Knowledge of Heart Failure

Next, I would like to find out how much you know about heart failure and its treatment. I'm going to read a question and some possible answers. Tell me which answer you think is correct. If you don't know the answer, you can just say "I don't know."

1. Heart failure means that: **Variable name: meaning**

- a. your heart is beating out of rhythm
- b. your heart might stop beating sometime soon
- c. your heart is not pumping blood as well as it should,
- d. you are having a heart attack

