- a. more fluids than usual
- b. about the same amount of fluids
- c. less fluids than usual
- d. DON'T KNOW

15. Someone with heart failure should weigh himself or herself: Variable name: wtfreq

- a. every day
- b. once a week
- c. once a month
- d. only if he or she feels badly
- e. DON'T KNOW

Self-Care Behaviors (Self-Care of Heart Failure Index or SCHFI)

Now, think about how you have been feeling in the **last month** as you respond to these questions.

SECTION A: Listed below are common instructions given to persons with heart failure.

How routinely do you do the following?	Never or rarely	Sometimes	Frequently	Always or daily
1. Weigh yourself? weigh_self	1	2	3	4
2. Check your ankles for swelling? check_ankles	1	2	3	4
3. Try to avoid getting sick (e.g., get a flu shot, avoid ill people)? avoid_sick	1	2	3	4
4. Do some physical activity? phys_activity	1	2	3	4
5. Keep doctor or nurse appointments? keep_appts	1	2	3	4
6. Eat a low salt diet? eat_low_salt	1	2	3	4
7. Exercise for 30 minutes? exercise	1	2	3	4
8. Forget to take one of your medicines? forget_meds	1	2	3	4
9. Ask for low salt items when eating out or visiting others? ask_lowsalt	1	2	3	4
10. Use a system (pill box, reminders) to help you remember your medicines? med_system	1	2	3	4

SECTION B: *sectionb_score*

Many patients have symptoms due to their heart failure. Trouble breathing and ankle swelling are common symptoms of heart failure. *Variable name: schfib_adequate*

In the past month, have you had trouble breathing or ankle swelling? (circle one) *Variable name: trouble*

- 0) No
- 1) Yes

11. If you had trouble breathing or ankle swelling in the past month... (circle one number) *Variable name: freq_trouble*

12.

	Have not had these	I did not recognize it	Not Quickly	Somewhat Quickly	Quickly	Very Quickly
--	--------------------	------------------------	-------------	------------------	---------	--------------

How quickly did you recognize it as a symptom of heart failure? Variable name: quick_recognize	N/A	0	1	2	3	4
--	-----	---	---	---	---	---

Listed below are remedies that people with heart failure use.

If you have trouble breathing or ankle swelling, how likely are you to try one of these remedies? (circle one number for each remedy)	Not Likely	Somewhat Likely	Likely	Very Likely
13. Reduce the salt in your diet reduce_salt	1	2	3	4
14. Reduce your fluid intake reduce_fluid	1	2	3	4

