3. I went into great detail about my medical symptoms [detailed_sxs2](#)

Strongly disagree									Strongly agree
0	1	2	3	4	5	6	7	8	9

4. I asked the doctor to explain the treatment or procedure in greater detail [explain_tx2](#)

Strongly disagree									Strongly agree
0	1	2	3	4	5	6	7	8	9

5. I offered opinions to the doctor [offer_opinions2](#)

Strongly disagree									Strongly agree
0	1	2	3	4	5	6	7	8	9

6. I expressed concerns to the doctor [express_concern2](#)

Strongly disagree									Strongly agree
0	1	2	3	4	5	6	7	8	9

Perceived Efficacy in Interacting with Doctor

Next, I'd like to ask you some questions about your interactions with your doctor.

1. **How confident are you in your ability to know what questions to ask a doctor?** *know_to_ask2*

Not at all confident 0	1	2	3	Very confident 4
---------------------------	---	---	---	---------------------

2. **How confident are you in your ability to get a doctor to answer all of your questions?** *get_answers2*

Not at all confident 0	1	2	3	Very confident 4
---------------------------	---	---	---	---------------------

3. **How confident are you in your ability to make the most of your visit with a doctor?** *maximize_visit2*

Not at all confident 0	1	2	3	Very confident 4
---------------------------	---	---	---	---------------------

4. **How confident are you in your ability to get a doctor to take your health concerns seriously?** *take_serious2*

Not at all confident 0	1	2	3	Very confident 4
---------------------------	---	---	---	---------------------

5. **How confident are you in your ability to get a doctor to do something about your health concerns?** *make_dr_act2*

Not at all confident 0	1	2	3	Very confident 4
---------------------------	---	---	---	---------------------

6. **How confident are you in your ability to ask a doctor questions?** *able_to_ask2*

Not at all confident 0	1	2	3	Very confident 4
---------------------------	---	---	---	---------------------

1-MONTH FOLLOW-UP PATIENT QUESTIONNAIRE

1-Month Follow-up Measures

1. Self-care behaviors (Same measure as at baseline)
2. Self-efficacy related to self-care (Same measure as at baseline)
3. Communication with provider (Same measure as at baseline)
4. Emotional support
5. Tangible support
6. Perceived efficacy in interacting with doctor

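### Patients meet the SCHFI straight after a 15-item heart-failure quiz at baseline but without it at 1 month, so question context is confounded with time

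*Combined protocol and SAP*

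**What the plan says.** **Patient baseline (section 4, baseline questionnaires).** The list of measures places "5. Knowledge of heart failure" immediately before self-care behaviors, which is item 6. The script agrees. The quiz starts with "Next, I would like to find out how much you know about heart failure and its treatment" and ends with "15. Someone with heart failure should weigh himself or herself: Variable name: wtfreq". The next block is "Self-Care Behaviors (Self-Care of Heart Failure Index or SCHFI". Its Section A is introduced by "Listed below are common instructions given to persons with heart failure", and its first item is "1. Weigh yourself".

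**Companion baseline (same section).** The list has "4. Knowledge of heart failure" followed by caregiver care behaviors as item 5.

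**1 month (section 4.2, 1-month follow-up measures).** The patient list has six measures. The first is "Self-care behaviors (Same measure as at baseline". No knowledge measure is listed. There is no separate 1-month list for companions.

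**Design and analysis.** Section 3.1 describes one group measured before and after. Section 6.2 lists the SCHFI subscales, and the caregiver counterpart, as secondary endpoints. Section 6.3 plans paired t-tests from baseline to 1 month and effect sizes for future proposals, and says that hypothesis testing is not being conducted. Knowledge is not an outcome in either section.

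**The concern.** A pre-post difference is interpretable only if the instrument is presented in the same way both times. Here the items are the same, but what the patient has just been asked is not. At baseline the patient has just answered 15 questions about heart failure, several on the behaviours the SCHFI then asks the patient to self-rate. At 1 month, on the listed order, the SCHFI comes first.

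If the quiz changes how patients rate themselves, that shift is present at one reading and absent at the other, so it enters the mean change in full. There is no control group and no variation in order planned within a time point, so the data cannot reveal it. At stake are the SCHFI change scores and the effect sizes taken forward to plan a later study.

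**Working it through.** The plan states no figure on this point, so there is none to reproduce. The check compares the questionnaire orders and then shows, under stated assumptions, how an artefact would pass into the result.

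**1. Order at the two time points (patients)**

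| | Baseline | 1 month |
|---|---|---|
| Knowledge quiz | 5th in list, 15 items | not listed |
| Self-care behaviors | 6th, directly after the quiz | 1st |

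The quiz count is 15; the seventh item has lost its printed number, but its variable is there. For these blocks the baseline list and the baseline script agree.

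**2. Overlap in content**

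- Direct: the last quiz item asks how often to weigh, with daily weighing as the first option. The first SCHFI item asks how routinely the patient weighs.
- Fairly close: the four SCHFI remedies (salt, fluid, an extra water pill, calling the clinic) each have a quiz item on the same subject (items 11, 14, 13 and 12).
- Looser: the quiz treats ankle swelling as a sign of worsening and asks about the response to leg swelling, not about checking ankles. It treats salt as a cause of worsening and does not ask about requesting low-salt food when eating out.

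**3. What a shift would do to the maintenance score**

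Inputs from the documents: ten Section A items scored 1 to 4, so the raw range is 40 − 10 = 30. Assumptions: rescaling to 0–100 (the documents give no scoring rule) and the item shifts.

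Score shift = (number of items × shift per item) / 30 × 100.

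| Shift per item | Weighing item only | Four items (weighing, ankles, low-salt diet, asking for low-salt items) |
|---|---|---|
| 0.1 | 0.3 | 1.3 |
| 0.25 | 0.8 | 3.3 |
| 0.5 | 1.7 | 6.7 |

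For scale, with 30 patients (the section 3.3 maximum of 30 dyads) and an assumed change SD of 15 points, the 95% half-width for the mean change is 2.045 × 15 / √30 = 5.6 points. Only the largest four-item scenario exceeds it.

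**4. What an artefact would do to the paired t-test**

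Assumptions: no true change, two-sided 5% level, artefact d in SDs of the change score. The rejection probability comes from the noncentral t distribution with n − 1 degrees of freedom and noncentrality d√n; for example, 0.2 × √30 = 1.10.

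| n | d = 0.1 | d = 0.2 | d = 0.3 |
|---|---|---|---|
| 15 | 6.5% | 11.2% | 19.2% |
| 20 | 7.1% | 13.6% | 24.7% |
| 30 | 8.3% | 18.5% | 35.5% |

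The estimated mean change is displaced by d SDs whatever the sample size. At n = 30 the 95% half-width is 2.045 / √30 = 0.37 SD, so artefacts of 0.1 to 0.3 SD lie within sampling error and would not stand out.

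**The case against.** **No effect is demonstrated.** A reader might infer that an order effect is certainly present, or that it raises baseline scores and so hides improvement. The documents support neither. They show a difference in context, not its consequence. The quiz could raise self-ratings by prompting desirable answers, or lower them by making gaps salient. The script has no step that tells patients the correct answers. This objection stands and limits the point to a risk of bias.

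**Part of the cue is present both times.** The SCHFI's own introduction already presents its items as recommended behaviours, and the same measure is used at 1 month. Only the quiz's added influence matters, and nothing in the documents sizes it. This lowers the weight but does not make the contexts equal.

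**The evidence on order is incomplete.** The 1-month order comes from a numbered list, not a full script, and lists here are not always exact: the 2-day list names self-efficacy for self-care, but the 2-day instrument shows no such block. The baseline survey may also be interrupted and finished after the visit or by phone that week (section 4), so quiz and SCHFI may be separated for some patients. That makes context vary at baseline; it does not align it with 1 month.

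**Companions.** A reader might extend the finding to them. The baseline order is the same, but with no 1-month companion list the contrast is not shown.

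**Low stakes.** This is a pilot whose primary outcome is enrollment, and its change estimates are already imprecise and uncontrolled. That is correct and keeps the priority modest. The planning effect sizes are still exposed.

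**Conclusion.** The point holds as a risk of bias. For patients, the documents place the quiz directly before the SCHFI at baseline and list no quiz at 1 month. Context and time are therefore confounded, and the single-group design cannot separate an order effect from change after the intervention.

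Size and direction are unknown. The figures in the working are conditional on assumed item shifts, an assumed SD, an assumed 0–100 scoring and an assumed 5% level; they show what an artefact could do, not what it will do. The four-item scenario also gives looser topic matches the same shift as weighing, which is generous.

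The exposure is confined to secondary SCHFI change scores and the effect sizes derived from them. The primary enrollment endpoint is unaffected. This is a cheap improvement worth making, not a flaw that undermines the pilot.

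**What to change.** In the patient and companion baseline questionnaires, move the knowledge quiz after all scales that are repeated at 1 month, just before demographics. Ask the repeated scales in the same relative order at both time points. At present the patient baseline asks perceived efficacy before the support questions, while the 1-month list puts it after them.

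The cost is re-ordering blocks in REDCap and on the paper form, with no added items or time. One downside is that SCHFI items may slightly cue the quiz answers; this matters little because knowledge is not a listed outcome. The move also leaves the companion, closeness and health-literacy blocks ahead of self-care at baseline only, but these do not ask about self-care behaviours.

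If baseline collection has begun, do not change the order midway. Either keep it and report the difference in question context as a limitation of the SCHFI change scores, or repeat the quiz before the SCHFI at 1 month, which adds 15 items to that call.
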